## I. BACKGROUND and RATIONALE

Stress urinary incontinence (SUI) is the complaint of involuntary loss of urine on effort or physical exertion, or on sneezing or coughing(1). In a recent epidemiological study of pelvic floor disorders in US women, 25% reported the presence of at least one pelvic floor disorder (urinary incontinence, prolapse, and fecal incontinence), of which 17% reported symptomatic urinary incontinence(2). As SUI is the most common of female pelvic disorders, it was estimated in a cost analysis that \$1.3 billion is spent on treatment of urinary incontinence annually, with SUI accounting for 82% of that cost(3). SUI can be managed by non-operative and operative therapy. Traditionally, first line therapy has consisted of non-operative interventions, which include behavioral therapy with pelvic floor muscle training or the use of a continence pessary. These interventions are less invasive and can be cost effective to the patient when compared to surgical intervention.

Continence pessaries are inexpensive, reusable vaginal inserts made of flexible silicone that are typically fit by a trained clinician in the office and managed by either the patient or the clinician. They come in various sizes and shapes to conform to a patient's vaginal cavity and provide structural support to the urethra. In a multi-centered randomized controlled trial of non-surgical management of SUI, 40% of participants in the continence pessary group reported "much better" or "very much better" SUI symptoms at 3 months, with 46% having greater than a 75% reduction in weekly urinary incontinence episodes (4).

In 2014, the FDA approved an over-the-counter disposable intravaginal device as another nonsurgical treatment for SUI. This device, the Poise Impressa®, is made of a non-absorbable nylon mesh that covers a core with 4 support poles made of resin and is housed in an applicator, similar to that of a tampon applicator(5). It is currently marketed as an over the counter non-surgical treatment of SUI, providing an effective alternative to physical therapy or surgery(6). Ziv et al conducted the initial study on this device, examining it over a 28 day period (comprised of a 14 day trial run followed by a 14 day observation period)(5). The authors found that 85% of participants experienced a  $\geq 70\%$  reduction in pad weight when using the device over the 14 day observation period. They also found that Poise Impressa® use was associated with an improvement in quality of life and had high patient satisfaction (5, 7).

The differences in these two devices are important and may result in major differences in patient satisfaction, compliance, and cost of use. The Poise Impressa® can only be worn up to 12 hours per day and is single use only, whereas the continence pessary can be worn continuously and is both reusable and reimbursable by insurance. To date, there has not been a comparative effectiveness trial performed to address this gap in knowledge. We aim to conduct a randomized comparative effectiveness trial of the continence pessary and the Poise Impressa® in order to provide patients and providers knowledge of the best nonsurgical treatment for women with SUI. We hypothesize that a physician fit continence pessary will provide greater subjective improvement in SUI symptoms, greater improvement in quality of life, greater patient satisfaction, and be lower cost as compared to the Poise Impressa®.

## II. SPECIFIC AIMS

**Specific Aim 1: To compare SUI symptom improvement between a continence pessary and the Poise Impressa® device.** Improvement will be assessed using the Patient Global Impression of Improvement (PGI-I), a validated questionnaire assessing symptom changes(8).

**Specific Aim 2: To compare quality of life, patient satisfaction, ease of device use, likelihood of continued use, and rates of adverse events between the continence pessary versus the Poise Impressa®.** We will use validated questionnaires to assess participants' quality of life (9, 10). We will monitor for adverse events that are related or possibly related to the study device such as pain, vaginal bleeding, infections, and lacerations. We will use a Likert scale to assess patient satisfaction, ease of device use, comfort, and likelihood of continued use.

**Specific Aim 3: To evaluate cost of use associated with each device.** We will use cost of clinic visits and the cost of the device(s) to calculate estimated costs associated with device utilization.

## III. METHODS

### Experimental Design

This is a multi-centered randomized controlled trial of women with stress urinary incontinence or stress predominant mixed urinary incontinence who desire non-surgical therapy.

### Study Population

#### Inclusion criteria:

- Female

- Age  $\geq$  21 years old based on Poise Impressa® manufacturing recommendations
- Pure stress urinary incontinence or stress predominant mixed urinary incontinence as determined by the Medical, Epidemiologic, and Social Aspects of Aging (MESA) Questionnaire (11). The MESA is a 16-item validated questionnaire intended to be utilized as a diagnostic questionnaire to evaluate SUI and urge urinary incontinence (UII). 9 questions assess SUI and 7 assess UII. Patients with scores in both categories are compared and the category with the highest score is identified as the predominant type of urinary incontinence.
- English-speaking

Exclusion criteria:

- Pregnancy. If patient is of childbearing potential and not using contraception a urine pregnancy test will be completed.
- Current urinary tract infection (UTI). Prior to enrollment all patients will have a urine dipstick performed. The presence of small/1+ or greater leukocytes and/or positive nitrites will require a urine culture to rule out infection. If the urine culture is positive (defined as  $>100,000$  CFUs), the participant must be treated. After completing antibiotic therapy the participant will have repeat urine dipstick performed and if negative then the participant can proceed with baseline data collection. If repeat urine dip is positive (per same criteria as above) or the patient is symptomatic for a UTI, a repeat urine culture will be obtained in 2 weeks and the same steps followed before participant can be included in the study.
- Current vaginal infection based upon symptoms and/or clinician findings. Participants may be treated for vaginal infection and then proceed with baseline data collection once treatment is completed and they are symptom free.
- Currently taking overactive bladder medications. Participants may choose to discontinue overactive bladder medication. Upon successful completion of a 3-week washout period, they may proceed with baseline data collection.
- Received intradetrusor onabotulinum toxin A within the past 12 months.
- Underwent peripheral tibial nerve stimulation for OAB in the past 12 months.
- Previous sacral nerve stimulation implantation (InterStim) for current OAB treatment.
- Prior stress urinary incontinence surgery (i.e. midurethral sling or burch urethropexy)
- Postmenopausal bleeding of unknown etiology
- Neurogenic bladder
- Urinary retention (PVR $>150$  mL obtained via bladder scan or catheterization)
- Pelvic organ prolapse past the hymen as assessed by POP-Q examination (point Ba, C, D, or Bp  $> 0$ cm)
- Inability to complete questionnaires in English or comply with study protocol
- Inability to insert/remove an intravaginal device independently
- Significant symptomatic vaginal atrophy based on clinician findings. Patient may be treated and then re-evaluated for inclusion.
- Prior treatment or experience with either continence pessary or Poise Impressa®.

**Interventions**

Continence pessary

Participants will be fit for a continence pessary at a fitting appointment by their clinician as per their office protocol. Only continence rings or continence dish pessary will be used. Participants will be instructed on how to remove and reinsert the device so that they can use it at their discretion. Participants will be allowed to use the device during the menses if they desire. They will however be instructed to take the device out during sexual activity. Participants will return to the office at 2 weeks, +/- 4 days for a follow-up visit for assessment and refitting if needed per routine clinical practice. If they feel that the continence pessary needs to be refit, the participants will be asked to call for an earlier follow-up appointment per routine clinical practice.

Poise Impressa®

Participants will be given a sizing kit in the office and asked to select the size that they feel is appropriate per manufacturer's instructions. Once they have selected a size, they will be given a 2-week supply of their size. They will be asked to follow directions on use per the packet insert to simulate "real world use." The packet insert does reflect when the device is not to be used. This includes participants not using this during sexual activity or during their menses. Participants will return to the office at 2 weeks, +/- 4 days for a research visit to assess fit and if needed, change to a different size. At this visit they will be given the remainder of their device supply to complete the study. If they feel that they need a different size, the participants will be asked to contact the research staff for an earlier follow-up visit. Participants may use this device for up to 12 hours in a 24-hour period per the manufacturer's recommendation. As we are assessing efficacy in the setting of typical use, participants will be asked to use this device as they normally would if they were to purchase this on their own for the management of SUI.

**Outcome Measures**

Baseline demographics and characteristics will be extracted from the patient's electronic medical record including age, past medical, surgical, obstetric and gynecologic history, menopausal status, and hormonal therapy. The presence or absence of pelvic organ prolapse will be assessed via a pelvic organ prolapse quantification (POP-Q) examination that has to have been performed within one year of enrollment. Participants will be observed for 4 weeks and will complete validated questionnaires and a 3-day bladder diary to assess response to treatment.

**Primary outcome:** Success in SUI treatment defined as a response of "very much better" or "much better" on the Patient Global Impression of Improvement (PGI-I) (8). The PGI-I is a validated questionnaire assessing a patient's global improvement in symptoms following a specific intervention. Patients will be asked "Check the answer that best describes how your stress urinary incontinence is now, compared with how it was before you began using the continence device in this study." It is based on a 7-item Likert scale including "very much better," "much better," "a little better," "no change," "a little worse," "much worse," and "very much worse."

**Secondary outcomes:**

**Quality of life (QoL):** Participants' QoL will be assessed with the following three validated questionnaires:

1. Urogenital Distress Inventory (UDI-6)(9, 12): This short form 6-item questionnaire measures urinary incontinence symptom bother.
2. Urinary Incontinence Impact Questionnaire (IIQ-7)(9, 12): This short form 7-item questionnaire measures the functional impact of urinary incontinence.
3. Female Sexual Function Index (FSFI)(13): This 19-item questionnaire is used to assess sexual functioning in women.

These questionnaires will be completed by participants at baseline and then again at the end of the 4-week study period. A change score will be calculated by subtracting the two scores.

**Interval Study Questionnaire:** Participants will complete this questionnaire at weeks 2 and 4. It consists of questions addressing menstrual status, device use, adverse events, and Likert scale questions assessing *device satisfaction, ease of use, comfort, and likelihood of continued use*. The questions will consist of the following:

- "Did you have your period during the last 2 weeks?"
  - If yes, "During the last two weeks, how many days were you on your period?" and "During the last two weeks, how many days did you wear your device?"
- "On average, how many hours a day did you wear your device?"
- "How satisfied were you with the device?" Participants may respond with "completely satisfied," "somewhat satisfied," or "not at all satisfied," "(14)." Responses include "completely comfortable," "somewhat comfortable," "not at all comfortable."
- "In general, how comfortable is the device?" Responses include "completely comfortable," "somewhat comfortable," "not at all comfortable."
- Ease of use will be assessed by asking "how easy/difficult was the device to use?", "how easy/difficulty was the device to insert?" and "how easy/difficult was the device to remove?" Responses will include "very easy," "easy," "somewhat easy," "somewhat difficult," "difficult," "very difficult."
- Likelihood of continued use will be assessed using the same Likert scale ranging from "strongly disagree" to "strongly agree" and asking participants to rate their level of agreement with the statement "I would continue to use this device in the future."
- Participants will also be asked, "If you had a friend or family member with stress urinary leakage, would you recommend this device to them?" Responses included "definitely would recommend," "probably would recommend," neutral or unsure," "probably would not recommend," "definitely would not recommend."
- Participants will also be asked if they have experienced any of the following: vaginal discomfort/pain, vaginal bleeding, vaginal infection, vaginal abrasion or laceration (cut in the vaginal tissues), urinary tract infection (bladder infection), other (with space to write in a response)

Additionally, participants will receive a phone call at 6 months during which general information regarding current device use and satisfaction will be collected via the follow-up questionnaire below. The PGI-I will also be administered verbally during these follow-up calls.

**Follow-Up Questionnaire:** Participants will complete this questionnaire at 6 months with a follow up phone calls and asked to respond to the following questions:

- "Are you still using the device provided to you during the study?"
  - If "yes", they will be asked "How satisfied are you with your current treatment?" Responses include "completely satisfied", "somewhat satisfied", or "not at all satisfied"
  - If "no", they will be asked several questions including:
    - Why are you not using the device? (select all responses that apply): "the device was too difficult to use", "the device did not work", "the device was too expensive", "I am using a different treatment," "I am not bothered by my leakage" or "Other".

- Are you using another treatment? If yes, "what treatment are you using?" with options of pessary, impressa, physical therapy, surgery, other
- They will also be asked the PGI-I

[figure not shown]
**Adverse events (AEs):** Potential AEs of interest include vaginal pain attributed to device use, vaginal bleeding, vaginal infection, vaginal abrasion/laceration, and urinary tract infection. Participants will be instructed to call and report any/all adverse events to research personnel and clinical staff. All AEs will be reported to the IRB of the institution at which the AE occurred (if required by site reporting guidelines), recorded in the research database, and if needed the patient will be scheduled for a clinical assessment. AEs will be assessed at each clinical/research visit and reported with study outcomes.

[figure not shown]
**Cost analysis:** For the Poise Impressa® device, cost calculations will include cost of sizing kit and devices, as well as costs associated with any refits. For the continence pessary, cost calculations will include the cost of the device, initial fitting visit and any additional clinic visits. Cost will be extrapolated to estimate annual cost of use for each device.

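### The adverse-event item on vaginal bleeding does not exclude menses, so a period could be reported and counted as an adverse event in the Aim 2 comparison (minor)

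*Combined protocol and SAP*

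**What the plan says.** All references are to the combined protocol and SAP.

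- **Specific Aim 2** compares "likelihood of continued use, and rates of adverse events between the continence pessary versus the Poise Impressa" groups, and sets the scope of monitoring: "We will monitor for adverse events that are related or possibly related to the study device such as pain, vaginal bleeding, infections, and lacerations".
- **Secondary outcomes, Interval Study Questionnaire** (weeks 2 and 4) describes the self-report checklist: "Participants will also be asked if they have experienced any of the following: vaginal discomfort/pain, vaginal bleeding, vaginal infection", followed by abrasion or laceration, urinary tract infection and a free-text option. The description gives no menses exclusion and no question on relation to the device.
- **Secondary outcomes, Adverse events** repeats the bare term: "Potential AEs of interest include vaginal pain attributed to device use, vaginal bleeding, vaginal infection, vaginal abrasion/laceration, and urinary tract infection". Only pain is tied to the device. The paragraph adds that "AEs will be assessed at each clinical/research visit and reported with study outcomes".
- **The same questionnaire** asks "Did you have your period during the last 2 weeks" and, if so, "During the last two weeks, how many days were you on your period".
- **Study Population** admits women from age 21 with no menopausal restriction and provides for pregnancy testing.
- **Interventions** treats menses differently by arm. For the pessary, "Participants will be allowed to use the device during the menses if they desire"; Impressa users follow the package insert, which rules out use during menses.

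No section says how the period answers are used to classify a bleeding report, or who judges relation to the device and how.

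**The concern.** The item collects something broader than the aim. Aim 2 concerns events that the device may have caused, whereas the checklist asks about bleeding from any cause in a population where some participants will have a period during the four weeks. A participant who takes the question literally could answer yes for an ordinary period.

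If such answers are counted, both devices appear to cause more bleeding than they do, and a real difference between them is harder to see. If women in one arm are more likely to report a period as bleeding, for example because they wear the device during menses and see blood on removing it, the comparison is biased in a direction that cannot be known in advance. Bleeding is a named safety outcome in a head-to-head device trial, so its rate should mean what readers will take it to mean.

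**Working it through.** **The plan's own figure.** The documents give no number for bleeding or menses, so the only figure to reproduce is the sample size, which supplies the number of evaluable women. The Sample Size Estimate gives 50% vs 25%, 80% power, 5% alpha (taken as two-sided) and 20% dropout. With unpooled variance:

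(1.960 + 0.842)² × (0.25 + 0.1875) / 0.25² = 55 per arm; 55 / (1 − 0.20) = 69 per arm, 138 in total.

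This matches the plan. The point raised here does not affect it.

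**Equal contamination.** Let p be the true rate of device-related bleeding and f the chance that a woman without it ticks the item because of a period. So f is the share of women with a period times the share of those who would tick; 20% × 25% gives f = 5%, and 40% × 50% gives f = 20%. The observed rate is

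p + (1 − p) × f.

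All p and f values are assumptions. Power is for a two-sided 5% normal-approximation test of two proportions (pooled variance under the null), 55 per arm, with every tick counted.

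| f | Observed, true 5% | Observed, true 20% | Difference (points) | Risk ratio | Power |
|---|---|---|---|---|---|
| 0 | 5.0% | 20.0% | 15.0 | 4.00 | 67% |
| 5% | 9.8% | 24.0% | 14.3 | 2.46 | 51% |
| 10% | 14.5% | 28.0% | 13.5 | 1.93 | 41% |
| 20% | 24.0% | 36.0% | 12.0 | 1.50 | 28% |

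With true rates of 10% and 30% instead, power goes from 75% (f = 0) to 65%, 56% and 42% at the same values of f.

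**Unequal contamination.** Take f = 20% in the pessary arm and 10% in the Impressa arm, again by assumption.

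- True rate 5% in both arms: pessary 0.05 + 0.95 × 0.20 = 24.0%; Impressa 0.05 + 0.95 × 0.10 = 14.5%. A difference of 9.5 points appears where there is none.
- True rate 5% pessary, 20% Impressa: pessary 24.0%; Impressa 0.20 + 0.80 × 0.10 = 28.0%. A true difference of 15 points shrinks to 4.

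**What the period questions can recover.** There are two cases for a bleeding report in a two-week window.

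1. No period in the window: the report is not menstrual. The existing questions settle it.
2. A period in the window: the report may be the period, device-related bleeding, or both. A count of period days does not say which.

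Discarding every case 2 report removes the contamination but also loses true events. Suppose a share m of women have a period and their bleeding reports are dropped, so that each true rate becomes p × (1 − m), still with 55 per arm. For 5% vs 20%, the rates are 3.5% vs 14% at m = 30%, 3% vs 12% at 40% and 2.5% vs 10% at 50%. Power is about 50%, 43% and 37%, against 67% for a clean item.

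**The case against.** The plan has several provisions that work against the problem. The questionnaire description puts the period questions ahead of the adverse-event list, so a woman has already declared her period when she reaches it, and many would then not report it again. Aim 2 limits events to those related or possibly related to the device, so a tick is not automatically an Aim 2 event. Staff assess adverse events at visits, every participant has a pelvic examination at week 4, and menopausal status is collected at baseline. The form itself is not in the documents: most items are quoted word for word, but the adverse-event item is only described, so its final wording may be better than the description.

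Much of this stands. A reader might infer that the bleeding comparison is diluted as a matter of fact, or that the period questions are no help at all. The documents support neither. Dilution needs women to report periods as bleeding and the study to count those reports; neither is shown, and reports from women without a period in the window are unambiguous.

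The safeguards still leave a gap. The relatedness limit is a scope with no procedure behind it. The adverse-event list that staff would work from has the same bare term. The week 4 examination is aimed at abrasions, lacerations and infections, and the plan does not say how it would attribute bleeding recalled from earlier weeks. None of these is designed to separate the two sources of bleeding when both fall in the same two weeks.

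**Conclusion.** The point holds as a risk in the instrument: as described, the checklist and the adverse-event list allow menses to be counted as vaginal bleeding, and for women with a period in the window the form's answers cannot resolve this afterwards. Equal counting in both arms would inflate the rates and pull the comparison towards no difference. Unequal counting could create, exaggerate or hide a difference.

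The size is unknown. The power figures depend wholly on assumed bleeding and misreporting rates and on no filtering; as f approaches zero, the loss disappears. A reader might also infer that the plan concedes this comparison is underpowered. The Sample Size Estimate says only that secondary outcomes in general may be.

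The severity is minor. One component of one secondary safety outcome is affected; the primary outcome and the sample size are not.

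**What to change.** Word the checklist item as *vaginal bleeding or spotting other than your period*. Use the same definition for vaginal bleeding in the adverse-event list under Secondary outcomes and when staff record events at visits. State that only non-menstrual bleeding counts towards the Aim 2 rate.

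The cost is a few words on one form and in one definition, with no added visit or procedure. If forms with the present wording are already in use, write down before the data are examined how bleeding reports will be classified against the period answers, and report separately those from women with a period in the window. That limits the problem but does not recover device-related bleeding in those women, so the change of wording is preferable.

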#### **Sample Size Estimate**

We aim to detect a clinically significant difference of 50% improvement with continence pessary versus 25% with the Poise Impressa®. Assuming an 80% power, an alpha error of 5% and a 20% dropout rate we need 138 participants total (69 per group) to detect this difference. We plan to assess for differences in secondary outcomes between arms while acknowledging that we may be underpowered to detect significant differences in these outcomes.

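### Month-6 satisfaction is asked only of women still using the study device, so any comparison of it between arms is restricted to continuers selected after randomisation

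*Combined protocol and SAP*

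**What the plan says.** Under Secondary outcomes, the protocol describes a 6-month call in which "general information regarding current device use and satisfaction will be collected via the follow-up questionnaire below". The questionnaire opens with a routing question: "Are you still using the device provided to you during the study". The branches then differ.

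- Still using: "If 'yes', they will be asked 'How satisfied are you with your current treatment", with three possible answers.
- Stopped: "If 'no', they will be asked several questions including" the reasons for stopping, such as difficulty, lack of effect, cost, another treatment or no longer being bothered. No satisfaction item is listed.

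Use of another treatment is also asked, and for the global rating of improvement "The PGI-I will also be administered verbally during these follow-up calls", with no condition on device use. At weeks 2 and 4 the Interval Study Questionnaire asks "How satisfied were you with the device", again with no condition on continued use.

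Specific Aim 2 is "To compare quality of life, patient satisfaction, ease of device use, likelihood of continued use" and adverse events between the two devices. The Sample Size Estimate section adds: "We plan to assess for differences in secondary outcomes between arms". The Statistical Analysis section assigns chi-square or Fisher tests to categorical variables and states intention-to-treat for the primary outcome only.

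**The concern.** Randomisation makes the arms comparable as allocated. It does not make the women still using a pessary at month 6 comparable with those still using Impressa. Whether a woman continues depends partly on how satisfied she is, and the pressures to stop differ by arm. The Background says Impressa is single-use and the pessary reusable and reimbursable. Under Interventions, Impressa is supplied only to complete the four-week study, after which women would buy their own. After the week-4 visit, Impressa women can have a pessary fitting scheduled.

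Nothing elsewhere in the plan covers this. The Missing Data section deals with missing data and dropout. A woman who takes the call and is routed past the question is neither. No denominator is given for month-6 satisfaction.

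At stake is the long-term satisfaction result for one secondary aim. A comparison among users could show no difference, or the opposite order, when the devices differ across all women reached.

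**Working it through.** **Inputs.** The documents give no month-6 continuation, satisfaction or contact rates. All such rates below are assumptions. The plan's only related figure is the sample size, used here solely to choose a group size.

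**Plan's figure.** For 50% versus 25%, two-sided 5% (sidedness assumed), 80% power and unpooled variance:

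n = (1.960 + 0.842)² × (0.25 + 0.1875) / 0.25² ≈ 54.9, so 55 per arm; 55 / 0.80 = 68.75, so 69 per arm and 138 in total.

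This matches the plan. I take 55 per arm as reached at month 6; that number is also an assumption.

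**Check 1: users versus all women reached.** Let c be the share still using and s the share of users who are satisfied. The printed routing yields s. The share of all women reached who are both using and satisfied is c × s.

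| Assumed c (pessary, Impressa) | Assumed s | Users only | Using and satisfied, all reached |
|---|---|---|---|
| 60%, 30% | 70%, 70% | 70% v 70% | 0.60 × 0.70 = 42% v 0.30 × 0.70 = 21% |
| 60%, 30% | 60%, 80% | 60% v 80% | 0.60 × 0.60 = 36% v 0.30 × 0.80 = 24% |
| 50%, 50% | 60%, 60% | 60% v 60% | 0.50 × 0.60 = 30% v 30% |

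With 55 per arm, row 1 leaves about 33 and 17 users. Rounded to whole women, users only gives 23/33 v 12/17 (70% v 71%, Fisher p = 1.0). All women reached gives 23/55 v 12/55 (42% v 22%, p = 0.04). Row 3 shows no distortion.

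The last column combines continuation and satisfaction. In row 1 the whole 21-point gap comes from the assumed continuation rates, so it does not measure error in the satisfaction item itself.

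**Check 2: satisfaction alone.** Suppose all women were asked and 50% (pessary) versus 25% (Impressa) were satisfied. Suppose 90% of satisfied women continue in each arm, and vary the share of dissatisfied women who continue.

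Satisfied among users = 0.9p / (0.9p + u(1 − p)), where p is the share satisfied among all women and u the share of dissatisfied women who continue.

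| u (pessary, Impressa) | Pessary users satisfied | Impressa users satisfied | Order |
|---|---|---|---|
| 50%, 10% | 0.45 / 0.70 = 64% | 0.225 / 0.30 = 75% | reversed |
| 30%, 10% | 0.45 / 0.60 = 75% | 0.225 / 0.30 = 75% | tie |
| 30%, 30% | 0.45 / 0.60 = 75% | 0.225 / 0.45 = 50% | preserved |

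The reason is visible in the odds. Among users, the odds of being satisfied equal the odds among all women multiplied by 0.9/u. The true odds are 1 and 1/3, an odds ratio of 3 for the pessary. In row 1 the multipliers are 1.8 and 9, a ratio of 5 in favour of Impressa, which outweighs 3. In row 2 they are 3 and 9, a ratio of 3, which cancels it. In row 3 both are 3, and the odds ratio of 3 survives. What matters is whether continuation depends on satisfaction differently in the two arms.

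**The case against.** The strongest reply is that no between-arm test of month-6 satisfaction is written out. Aim 2 names no time point, its satisfaction measure is a Likert scale, and the Interval Study Questionnaire supplies one at weeks 2 and 4 for all participants. The month-6 call is introduced as collecting general information. On this view Aim 2 already has an unconditional satisfaction measure. That much stands: a month-6 test is an inference from Aim 2, the Sample Size Estimate and the generic methods. But the questionnaire sits under Secondary outcomes, and nothing limits the item to description.

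Two stronger readings are tempting and should be resisted.

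- A reader might infer that women who stop drop out of the evidence. They do not. They give satisfaction at weeks 2 and 4 and, at month 6, continuation status, reasons for stopping and the PGI-I. A device that most women abandoned would show up in the continuation rates, provided those are reported.
- A reader might infer that the device with more stopping is always favoured. The documents do not establish this. Dissatisfied women may continue, and satisfied women may stop because of cost or because leakage no longer bothers them. The last row of each table shows no distortion or a preserved order.

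It is also fair to say that the stopped branch is introduced with an open-ended phrase, so an unlisted satisfaction item cannot be excluded. None is stated.

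**Conclusion.** The concern holds in a limited form. As printed, month-6 satisfaction is measured only in continuers, and any comparison of it between arms lacks the protection of randomisation. It can be null or reversed relative to all women reached: for example 70% v 70% among users beside 42% v 21% using and satisfied, or 64% v 75% among users when satisfaction among all women is 50% v 25%. These sizes rest wholly on assumed rates. Distortion of the satisfaction odds ratio requires continuation to depend on satisfaction differently by arm. The supply and cost differences make unequal continuation plausible, but they do not fix the direction of any distortion.

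The primary outcome, satisfaction at weeks 2 and 4, month-6 continuation and month-6 PGI-I are unaffected. The change is worth making because it costs almost nothing.

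**What to change.** 1. In the Follow-Up Questionnaire, ask every woman reached at month 6 how satisfied she is or was with the study device, using the same three answers. Naming the study device also avoids a rating of some other current treatment.
2. In the Statistical Analysis section, state that month-6 satisfaction is compared between arms on that item, by randomised group, among all women reached.
3. Report satisfaction among continuers descriptively only, beside the continuation rate in each arm.
4. As a supporting analysis, report *still using and completely satisfied* (yes/no) among all women reached, labelled as a composite of continuation and satisfaction. This should not replace item 1, because it counts stopping for cost or lack of bother as a failure and groups somewhat satisfied users with the failures.
5. For item 4, word the continued-use question so that it covers women who bought more of the same single-use device. As printed it refers to the device provided in the study, and a woman who now buys her own Impressa could answer no.

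The cost is a few seconds on an existing call and a few sentences in the plan. No extra patients or visits are needed. Reported satisfaction percentages may be lower. Women not reached at month 6 remain missing and should be counted by arm.
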